7.5. Clinical Asthma Exacerbation

7.5.1. Clinical Asthma Exacerbation Definition

A CAE is the primary outcome measure of this study. In this study, a CAE is an occurrence of either a "severe CAE" or a "moderate CAE." defined as the following:

- A severe CAE is defined as a CAE that involves worsening asthma such that
 - the treating physician elects to administer prednisone (or equivalent glucocorticoid treatment) at least 10 mg prednisone equivalent above baseline (Table 2), for at least 3 daysAND
 - an unscheduled provider visit such as an office visit, urgent care visit, emergency care visit, or hospitalization
- A moderate CAE is defined as a CAE that involves worsening asthma such that
 - the treating physician elects to administer prednisone (or equivalent glucocorticoid treatment) at least 10 mg prednisone equivalent above baseline (Table 2), for at least 3 days

OR

- an unscheduled provider visit such as an office visit, urgent care visit, emergency care visit, or hospitalization associated with an increase in asthma therapy that does not qualify for “severe CAE” as defined above

Table 2: Systemic Glucocorticoid Treatment Equivalent to 10 mg of Prednisone

Glucocorticoid Treatment	Dose (mg) Equivalent to 10 mg of Prednisone	Comment
Cortisone	50	Includes parenteral
Hydrocortisone	40	Cortisol
Prednisolone	10	-
Methylprednisolone	8	Medrol: includes parenteral SOLU-MEDROL®
Triamcinolone	8	-
Betamethasone	0.4	-
Dexamethasone	0.4	Oral or parenteral DECADRON®

The designation of a CAE as moderate or severe is denoted by the response to the CRF question “Severity” on the Clinical Asthma Exacerbation CRF page regardless of whether the following CRF questions are answered in the negative or missing:

- “The treating physician elects to administer prednisone (or equivalent glucocorticoid treatment) at least 10 mg prednisone equivalent above baseline, for at least 3 days”
- An unscheduled provider visit such as an office visit, urgent care visit, emergency care visit, or hospitalization

A patient may experience more than 1 CAE during the study period.

Clinical Asthma Exacerbation Status: Clinical asthma exacerbation status is an indicator of whether or not a patient experienced a CAE during study follow-up (Yes, No).

Clinical Asthma Exacerbation Rate: The percentage of patients who experience at least 1 moderate or severe CAE at the end of study follow-up.

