Recurrent Clinical Asthma Exacerbation Rate: The percentage of patients who experience more than 1 moderate or severe CAE at the end of study follow-up.

Time to Clinical Asthma Exacerbation: Time, in days, from Study Day 1 to the Date of Symptom Peak plus 1.

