7.5.2.1. Within Patient CAE Analyses

For each CAE event occurring at least 2 weeks after baseline, device-use measures (albuterol use, inhalational flow [MIF], inhalational volume, and time to MIF) will be summarized for each of 2 weeks of interest: first- 'CAE-adjacent week', the week immediately preceding the onset of CAE symptom (ie, day 1 through 7 preceding the date of the CAE symptom onset), and second – 'CAE-Prior Adjacent week', the week preceding that week (ie, during day 8 through 14 preceding the date of the CAE symptom onset). Summary measures of daily and or weekly use will be compared between the two weeks, as proposed below:

Albuterol use measures:

- total number of inhalations in that week
- the maximal daily number of inhalations in that week
- the mean number of daily inhalations (ie, total number of inhalations divided by number of days with number>0)
- occurrence of a single day's albuterol use exceeding 4 inhalations;
- occurrence of a single day's albuterol use exceeding 8 inhalations
- occurrence of a single day's albuterol use exceeding 12 inhalations
- number of days when albuterol use exceeding 4 inhalations;
- number of days when albuterol use exceeding 8 inhalations
- number of days when albuterol use exceeding 12 inhalations

To note, in this analysis, no inhalation in any day will be taken as a 0 count.

Inhalation flow values parameters:

- maximal daily MIF during the week
- minimal daily time to MIF within a week
- maximal total daily inhalational volume within a week,

To note, if no inhalation was taken at a specific day, flow value parameters will be missing and will not be imputed.

Analysis will be based on all patients CAEs for which there are 14 days (or more) prior to the CAE onset, where patient has been on study and CAE free.

Descriptive statistics of use measures in the 'CAE-adjacent week' and 'CAE-Prior Adjacent week' will be presented.

Continuous measures will be compared between the 2 weeks using paired t-test (and Wilcoxon Signed Ranks test) whereas binary patterns will be compared using Mc-Nemar test.

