7.5.2.3. All Days Analysis (Only CAE-free Days)

This analysis will be performed by the data analytics group. Additional details may be specified in a separate report. One possible analysis is presented below:

For each patient, all study days where the patient was CAE free will be the unit of this analysis. There are various ways to summarize albuterol use on this, for example by looking at:

- daily number of inhalations:
- albuterol use exceeding 4 inhalations (Yes/No)
- albuterol use exceeding 12 inhalations (Yes/No)

Exploratory analyses using all these patient days can be performed to predict occurrence of CAE event in the next day (for example, using logistic regression). Exploratory predictive analyses will be reported separately.

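### SAP 7.5.2.1 tests repeat CAEs from the same patient as independent pairs, so its p-values can be somewhat too small

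*SAP*

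**What the plan says.** SAP 7.5.2.1 sets two 7-day windows before CAE symptom onset and lists twelve measures: nine of albuterol use and three of inhalation flow. "Summary measures of daily and or weekly use will be compared between the two weeks". The data set is defined by event: "Analysis will be based on all patients CAEs for which there are 14 days (or more) prior to the CAE onset", with the condition "where patient has been on study and CAE free". On the tests: "Continuous measures will be compared between the 2 weeks using paired t-test (and Wilcoxon Signed Ranks test", with McNemar's test for binary patterns. The section states no significance level, sidedness or confidence interval. It names no patient term, robust variance or limit of one CAE per patient.

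SAP 7.5.1 says: "A patient may experience more than 1 CAE during the study period". It defines a recurrent CAE rate, "The percentage of patients who experience more than 1 moderate or severe CAE at the end of study follow-up", without an expected value. SAP Section 8 plans no sensitivity analysis, and Section 9 no multiplicity adjustment.

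Two neighbouring analyses differ. SAP 7.1.2.3 tests a rise in albuterol use over similar windows, counted back from symptom peak, at the 0.05 level. It takes one difference per subject and allows for a random subject effect. SAP 7.5.2.3 describes a patient-day analysis in which "all study days where the patient was CAE free will be the unit of this analysis", introduced by "One possible analysis is presented below", with logistic regression as an example. It is left to the data analytics group and a separate report.

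**The concern.** Paired tests treat each pair as new, independent information. Two CAEs in one patient may not be. A patient whose albuterol use climbs steeply before one exacerbation may do the same before the next, while another patient may show little rise either time. Pairing removes the patient's usual level of use, but not a patient-specific pattern of change. If differences are positively correlated within patients, the effective number of pairs is below the number counted, the standard error is understated, and null device measures reach significance more often than the nominal rate.

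Recurrence is foreseeable. Entry requires a severe CAE in the previous 12 months (protocol 4.1). The rationale in protocol 16.2 for deleting an exclusion criterion says CAE risk is highest in the 30 days after an exacerbation. The SAP plans to report recurrent events (7.5.2.4) and to plot patients with multiple CAEs (7.1.2.2). With twelve measures, no multiplicity control and no sensitivity analysis, nothing else in the plan would reveal the problem.

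**Working it through.** **The plan's own figure.** SAP 2.3 has 400 enrolled and 10% dropout: 400 × 0.90 = 360. Then 360 × 0.20 = 72 and 360 × 0.25 = 90, which reproduces the 72 to 90 expected events. These are percentages of patients times patients. They count patients with a CAE and leave out repeats. No power or p-value is stated for 7.5.2.1, so there is none to reproduce.

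**Formula.** Let m be the number of eligible CAEs from a contributing patient and ρ the within-patient correlation of the differences. Then

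DE = 1 + (Σm²/Σm − 1) × ρ

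true two-sided error = 2 × [1 − Φ(1.96/√DE)], at a nominal 5% (assumed, since 7.5.2.1 states no level).

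**Worked example.** Take 72 patients, 58 with one eligible CAE and 14 with two, and ρ = 0.5.
- Σm = 58 + 28 = 86; Σm² = 58 + 56 = 114.
- DE = 1 + (114/86 − 1) × 0.5 = 1.163.
- Error = 2 × [1 − Φ(1.96/1.078)] = 0.069.

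**Check by simulation.** With 72 patients, 25% of them having a second CAE, and 6,000 runs per setting:

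| ρ | Formula | Paired t | Wilcoxon | McNemar | First CAE only (t) |
|---|---|---|---|---|---|
| 0.5 | 0.074 | 0.074 | 0.073 | 0.072 | 0.048 |
| 0.8 | 0.088 | 0.088 | 0.084 | 0.081 | 0.050 |

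The formula serves all three tests, and one CAE per patient restores the nominal rate. The 25% is for checking only; the next step shows it is too high for this section.

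**Applying the section's eligibility rule.** Only CAEs preceded by 14 on-study, CAE-free days enter. With 3-day CAEs, a patient can supply at most five in 84 days (onsets on days 15, 32, 49, 66 and 83). Inputs from the plan: 84 days and 20% to 25% of patients with any CAE. Assumptions: CAE duration 3 to 10 days, random event times, ρ from 0.2 to 0.8, and the recurrence model shown.

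| Recurrence model | Contributing patients with more than one pair | DE | True error |
|---|---|---|---|
| Poisson | 4–7% | 1.02–1.10 | 5.2–6.2% |
| Gamma-mixed, shape 1 to 0.5 | 8–18% | 1.03–1.28 | 5.3–8.3% |

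A hand check: if a share f of contributing patients has exactly two pairs, Σm²/Σm − 1 = 2f/(1 + f). At f = 0.04 and ρ = 0.2, DE = 1 + 0.077 × 0.2 = 1.015. At f = 0.18 and ρ = 0.8, DE = 1 + 0.305 × 0.8 = 1.24; patients with three or more pairs account for the rest of the way to 1.28. The true standard error is √1.02 = 1.01 to √1.28 = 1.13 times the one the tests use.

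**Patient-days (7.5.2.3 example).** A pooled logistic score test was simulated with a null predictor, 360 patients, 84 days, about 97 events and 1,500 runs per setting. Using all days, the error was 0.043–0.049 with no patient heterogeneity in CAE risk, 0.070–0.081 with log-risk SD 1.0, and 0.110–0.179 with SD 1.5. Using only days up to the first CAE, it was 0.044–0.053 in every setting. Inflation comes from repeat CAEs combined with heterogeneity, not from patient-days as such.

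**The case against.** The strongest reply is that the problem is small and the study exploratory. Pairing already removes each patient's level, so ρ is the correlation of changes, not of use, and nothing in the documents shows that it is high. The 14-day rule also removes most close recurrences: counting all CAEs would give 20–34% of CAE patients with repeats under the gamma models, against 8–18% of contributing patients after the rule. Both points stand and bound the size. Neither removes the defect: the rule prevents overlapping windows, not correlation between episodes, and the SAP itself uses one difference per subject for the closely similar contrast in 7.1.2.3.

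Some stronger readings are tempting but not supported:
- A reader might infer error rates up to 15%. That figure comes from counting every CAE (design effect up to 1.85) and ignores the section's eligibility rule.
- A reader might infer that confidence intervals are too narrow. Neither 7.5.2.1 nor 7.5.2.3 plans one.
- A reader might infer that the SAP analyses patient-days as independent. Section 7.5.2.3 offers an example, with no variance method fixed.
- A reader might infer that the hypothesis of rising use before a CAE is tested wrongly. Its test in 7.1.2.3 works at subject level, although it does not say which CAE supplies the difference when a patient has several.

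**Conclusion.** The point holds for SAP 7.5.2.1. Repeat CAEs enter paired t, Wilcoxon and McNemar tests as independent pairs without correction, so the p-values are too small if differences are positively correlated within patients. The effect is small to moderate. Its size rests on a recurrence pattern, CAE duration and correlation that the documents do not give; the low end is negligible, and the high end needs shape 0.5 and ρ = 0.8 together. This does not undermine the study's stated hypothesis test, but it is a plain mismatch of unit and test that is cheap to remove. For 7.5.2.3 the point is only a request that the separate report specify a suitable method.

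**What to change.** In SAP 7.5.2.1, choose one of two rules and state it:

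- Use each patient's first eligible CAE and keep the present tests. If no patient has more than two pairs, the loss is f/(1 + f): 0.04/1.04 = 4% to 0.18/1.18 = 15% of pairs over the range above.
- Keep all eligible CAEs with patient-clustered inference: a mixed model or GEE for continuous measures, and GEE or a clustered McNemar test for binary ones. No pairs are lost.

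Either way, report the number of patients and the number of CAEs beside each result. The separate report for 7.5.2.3 should use patient-clustered standard errors or only days up to the first CAE.

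The cost is a few sentences and standard procedures. SAP 2.4.2 has amendments approved before database lock; after SAP finalization, protocol Section 9 requires such a change to be disclosed and justified in the clinical study report.

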7.5.2.2. Time to Clinical Asthma Exacerbations Short-term Exacerbation Risk (7 days)

For each patient, the following 3 landmark use events will be identified:

- first time in study when had >4 inhalations per day ("low use group")
- first time in study when had >8 inhalations per day ("medium use group")
- first time in study when had >12 inhalations per day ("high use group").

A patient may be included in more than 1 landmark use group (for example, if had >12 inhalations a day any time during study, then on that time or already before he/she also had >8 and >4 a day).

For each landmark use groups, time to CAE within 7 days since the landmark event will be estimated and plotted using Kaplan-Meier plot. The 3 groups will be presented in the same plot, to assess a possible 'dose-response' association, if higher use is associated with shorter time to CAE.

If a CAE has not occurred within 7 days, then that observation will be censored at 7 days or earlier if follow-up had completed/terminated before 7 days elapsed. Note, if CAE occurred on the same date where landmark use happened, then time to CAE will be calculated as 0.

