9.5.2.1. Endpoint Analysis

The multiple device-use-measures will be used as predictors of CAE in the following stepwise selection logistic regression models to select significant predictors in a forward manner:

- 1. albuterol usage
- 2. albuterol usage + inspiratory flow values
- 3. albuterol usage + SDI

- 4. albuterol usage + TDS
- 5. albuterol usage + inspiratory flow values + SDI
- 6. albuterol usage + inspiratory flow values + TDS

Demographic variables and disease state information collected at study enrollment will also be considered as predictors. Because the device-use-measures will be collected continuously over time, these measures could be used to derive many potential predictors of risk. For example, with respect to albuterol use, a subject using the inhaler 3 times in the span of a 2-day or 3-day period could be a strong predictor of a CAE, but a better marker for risk might be 10 times in the span of a week. There are no prior robust data to inform these decisions; 1 possible benefit of this work will be to examine the relationship between multiple functional forms for the device-use-measures to determine which forms have predictive power.

Furthermore, the effect of including interaction terms in the model (ie, testing the assumption of additivity of predictors on the log odds scale) will also be studied. The primary hypothesis under consideration is that >12 inhalations of SABA dosing will have higher odds of CAE risk relative to 0 to 12 inhalations per day. This dosing scheme is consistent with the approved labelling for albuterol inhalation products. Pair-wise interactions will be assessed at the 0.01 significance level to avoid weak interaction signals that would potentially not translate when applying the risk score to new cohorts. Goodness-of-fit tests may be applied to make sure that the finally selected model fits the data closely. The C-statistic will be used to compare the goodness of fit of various logistic regression models in terms of how well the predictor(s) discriminate between patients with and without CAE (Hosmer et al 2013).

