MedDRA	Medical Dictionary for Regulatory Activities
MIF	maximal inhalational flow
mITT	modified intent-to-treat
PT	preferred term
R&D	Research and Development
SABA	short-acting beta agonist
SAMA	short-acting muscarinic antagonist
SD	standard deviation
SDI	sleep disruption index
SOC	system organ class
SOP	standard operating procedure
TDS	total daily steps
ULN	upper limit of normal
WHO Drug	World Health Organization Drug Dictionary

INTRODUCTION

This Statistical Analysis Plan describes the planned analysis and reporting for Teva Branded Pharmaceutical Products R&D, Inc. Study ABS-AS-30064 (A 12-Week, Open-Label Study to Evaluate the Relationship Between Use of Albuterol Multidose Dry Powder Inhaler with an eModule (eMDPI), an Inhaled Short-Acting Beta Agonist (SABA) “Rescue” Agent with an eModule, and Exacerbations in Patients (18 Years of Age or Older) with Asthma), and was written in accordance with standard operating procedure (SOP) GBP_RD_702 (Statistical Analysis Plan).

The reader of this Statistical Analysis Plan is encouraged to read the study protocol for details on the conduct of this study, the operational aspects of clinical assessments, and the timing for completing the participation of a patient in this study. The Statistical Analysis Plan is intended to be in agreement with the protocol. However, the Statistical Analysis Plan may contain more details regarding these particular points of interest, or other types of analyses (eg, other endpoints). When differences exist in descriptions or explanations provided in the study protocol and this document, the Statistical Analysis Plan prevails; the differences will be explained in the clinical study report (CSR) or in this document.

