2.4.2. Final Analyses and Reporting

All analyses identified in this Statistical Analysis Plan will be performed after the end of the study as defined in the study protocol.

This Statistical Analysis Plan and any corresponding amendments will be approved before database lock, in accordance with SOP GBP_RD_702 (Statistical Analysis Plan).

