7.5.3. Predicting Severe CAE/Moderate CAE from Multiple Device-Use-Measures

Predictive analysis will be performed by the data analytics group. Additional details may be specified in a separate report. Exploratory predictive analyses will be reported separately.

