20.4. Predicting Severe CAE/Moderate CAE from Multiple Device-Use-Measures

Statistical Analysis Plan Section	Protocol Section	Protocol Description	Statistical Analysis Plan Change	Rationale
7.5.3	9.5.2.1	The multiple device-use-measures will be used as predictors of CAE in stepwise selection logistic regression models to select significant predictors in a forward manner.	Predicative analysis will be performed by the data analytics group. Additional details may be specified in a separate report. Exploratory predictive analyses will be reported separately.	Clarification. Analysis was removed from the SAP as this analysis will be performed separately by the data analytics group.

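### The SAP's 7-day landmark plot can count albuterol use during an exacerbation as preceding it, and no analysis the SAP commits to estimates the protocol's >12 versus 0-12 odds contrast

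*SAP*

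**What the plan says.** **The landmark plot.** SAP 7.5.2.2 finds each patient's first study day above 4, above 8 and above 12 inhalations and draws three Kaplan-Meier curves of time to CAE over the next 7 days. A patient can be in more than one group, and the curves are to be read for a dose-response association. Censoring applies only when no CAE occurs within the window, and "if CAE occurred on the same date where landmark use happened, then time to CAE will be calculated as 0". Same-day CAEs are therefore events.

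**The CAE date.** Section 7.5.2.2 names none. SAP 7.5.1 defines time to CAE from Study Day 1 to the date of symptom peak, plus 1. SAP 7.5.2.1 counts back from symptom onset and requires at least 14 days on study and CAE-free. In 7.5.2.3, "all study days where the patient was CAE free will be the unit of this analysis".

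**The >12 contrast.** Protocol 9.5.2.1, within its logistic regression plan, states: "The primary hypothesis under consideration is that >12 inhalations of SABA dosing will have higher odds of CAE risk relative to 0 to 12"; both figures are daily counts. SAP 20.4 records of that regression: "Analysis was removed from the SAP as this analysis will be performed separately by the data analytics group". SAP 7.5.3 adds: "Additional details may be specified in a separate report. Exploratory predictive analyses will be reported separately". The patient-day model in SAP 7.5.2.3 is introduced with "One possible analysis is presented below". The SAP Introduction says: "When differences exist in descriptions or explanations provided in the study protocol and this document, the Statistical Analysis Plan prevails". On timing, SAP 2.4.2 says: "This Statistical Analysis Plan and any corresponding amendments will be approved before database lock".

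**The concern.** The study asks which patterns of use predict a later CAE. If reliever use climbs once symptoms have begun, a patient's first day above 12 may fall inside the exacerbation. Section 7.5.2.2 then treats that day as the warning and the same exacerbation as the outcome. The neighbouring sections guard against this by restricting to CAE-free time; 7.5.2.2 does not. The higher the threshold, the larger the share of first crossings that occur during a flare, so the three curves can separate in the expected order even if earlier use carries no information.

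The second issue is separate. The contrast that the protocol calls its primary hypothesis has no committed estimate in the SAP, and the SAP does not fix its unit of analysis or outcome window. The landmark plot cannot stand in for it: it has no 0-12 group and no test or effect estimate.

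**Working it through.** **1. The plan's own event count.** 400 x 0.90 = 360 evaluable patients. 360 x 0.20 = 72 and 360 x 0.25 = 90 CAEs; 360 x 0.067 = 24 moderate plus 360 x 0.15 = 54 severe gives 78. All agree with SAP 2.3. No figure is stated for the landmark plot or the >12 contrast.

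**2. Does the 7.5.1 definition settle the date?** Applied from the landmark, a same-day CAE would have time 0 + 1 = 1. Section 7.5.2.2 sets it to 0, so the definition does not fit as written. With onset dating, contamination enters only through the same-day rule. With peak dating, it can enter on any day from onset to peak.

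**3. Benchmark with no rise in use.** If CAEs fall uniformly over 84 days and use is unrelated to them, the chance of one 1-7 days after a landmark is about 78/360 x 7/84 = 1.8%. Counting the landmark day as well gives 78/360 x 8/84 = 2.1%. The same-day rule alone adds almost nothing.

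**4. Illustration with a rise only after onset.** Assumptions, none from the documents except 360 patients and 21.7% with a CAE: patient rates L are gamma (shape 1) with mean 3 per day; daily counts are Poisson; from onset to peak the rate becomes 2L + 1 or 4L + 3; the lag is 1, 3 or 5 days; 300 replicates. Earlier use predicts nothing. Percent of each landmark group with a CAE within 7 days, in two of the six settings:

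| Rise, lag | Landmark | Onset, same-day left out | Onset, same-day counted | Peak, same-day counted |
|---|---|---|---|---|
| 2L + 1, 1 day | >4 | 1.8 | 4.1 | 5.2 |
| | >8 | 1.8 | 6.8 | 9.3 |
| | >12 | 1.4 | 10.4 | 15.1 |
| 4L + 3, 5 days | >4 | 1.7 | 9.7 | 12.4 |
| | >8 | 1.4 | 19.5 | 27.8 |
| | >12 | 1.1 | 31.1 | 45.2 |

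Over all six settings the >12 group runs 1.0-1.7%, 10.1-33.8% and 15.1-45.2%. The upward gradient appears only in the last two columns.

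**5. A second set of inputs.** The cited cohort in Protocol 3.3 gives 5.5 (SD 9.7) actuations per day in 45 exacerbating patients and 1.83 (SD 3.3) in 102 others. The pooled mean is (45 x 5.5 + 102 x 1.83)/147 = 2.95, with SD 6.26. With 78 CAEs in 360 patients and an assumed lag of 1-3 days, the >12 group gives:

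| Use after onset | Onset, days 1-7 only | Onset, same-day counted | Peak, same-day counted |
|---|---|---|---|
| No rise | 1.8% | 2.0-2.1% | 1.7-1.9% |
| Doubled | 1.9% | 5.0-5.1% | 6.5-7.8% |
| 10% of onset-to-peak days above 12 | 1.7-1.9% | 10.2-11.8% | 20.4-30.0% |

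Keeping the two patient groups separate, so that earlier use does carry information, gives 4.0%, 4.2-4.4% and 3.2-4.0% with no rise, and 3.8-4.0%, 9.0-9.4% and 11.5-13.2% if use doubles.

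**6. Overlap of the groups.** With the same inputs, 130-138 patients have a >4 landmark before onset. Of these, 45-53 are also in the >12 group, and for 18-24 both landmarks fall on the same date, so the same follow-up is drawn in both curves.

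**7. Which committed SAP analyses use the 12-inhalation cut?**
- 7.5.2.1: a McNemar test of any day above 12 in the week before onset against the week before that. It covers CAE patients only and specifies no odds ratio.
- 7.1.2.4: days before peak for CAE patients, but proportion of days for CAE-free patients. These are different metrics and cannot be contrasted.
- 7.2.2.1, 7.3.2.1 and 7.4.2.1: flow, steps and sleep at the first day above 12, not CAE risk.
- 7.5.2.2: nested curves without a 0-12 group.

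Two neighbours do not use the cut. Section 7.1.2.3 tests for a rise before the peak in CAE patients, and 7.1.2.5 summarises the 24-hour maximum. None of these estimates the odds of CAE at >12 versus 0-12.

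**The case against.** The study is exploratory, its endpoints are not ranked, and the plot carries no test. The overlap of the groups is stated openly, and same-day CAEs sit visibly at time 0. This lowers the stakes, but a plot meant to show short-term risk should still not contain use that belongs to the exacerbation. The time-0 step also does not reveal landmarks between onset and peak if peak dating applies.

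Peak dating is not wrong in itself. Two of the protocol's three albuterol parameters are anchored at the peak of a severe CAE, and a CAE is defined by steroid treatment or an unscheduled visit, so rising use after onset may be a wanted signal. That stands, and it is a reason to allow a labelled peak-dated supplement.

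The McNemar test in 7.5.2.1 is anchored at onset and avoids the contamination. That also stands, so the plot is not the SAP's only look at use shortly before a CAE. But the test has no CAE-free comparator.

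A reader might infer that the sponsor dropped its primary hypothesis or left it to be chosen after seeing the data. The documents do not support this. The regression was moved, with the change and reason disclosed in SAP 20.4; the contrast and model family remain in the protocol; and the SAP amendment history refers to an ancillary analytics report. That report is not available here, and when it fixed the unit and window is unknown.

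**Conclusion.** Two points hold. First, as written, 7.5.2.2 can count use during an exacerbation as preceding it, most of all under peak dating, and can show a dose gradient when earlier use predicts nothing. The mechanism follows from the text, but the size does not. It depends on the rise in use after onset and the onset-to-peak lag, which the documents do not give. The simulated figures are illustrations, from no inflation (no rise) to a >12-group proportion of 45% where the clean figure is 1-2%. It would go too far to say that the SAP never dates a time to CAE: 7.5.1 does, at peak. The defect is that 7.5.2.2 does not say whether that definition applies, its plus 1 conflicts with the time-0 rule, and 7.5.2.1 uses onset.

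Second, no analysis the SAP commits to estimates the >12 versus 0-12 odds contrast, and the SAP fixes neither its unit nor its window. This should be fixed; confidence is medium.

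**What to change.** 1. In 7.5.2.2, state the CAE date and use symptom onset, as in 7.5.2.1. Count only landmark days that are CAE-free and before onset, start the clock the day after, and report same-day CAEs as a separate count. A peak-dated version may be shown as a labelled supplement.
2. Label the nested curves descriptive and do not read dose-response from them.
3. Before database lock, commit in 7.5.2.3 one logistic model on CAE-free patient-days for >12 versus 0-12, with CAE onset in days 1-7 as the single window. Use patient-clustered errors and report the odds ratio, 95% CI and 2x2 counts. Use exclusive categories 0-4, 5-8, 9-12 and >12 as a secondary coding for dose-response.

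Days 1-7 match 7.5.2.2 and are safer if days above 12 are rare. Suppose 0.3-1% of days are above 12 (assumed) and unrelated to CAE. With 78 CAEs, the chance of no exposed event in a next-day window is 0.997^78 = 0.79 to 0.99^78 = 0.46. Over 78 x 7 = 546 pre-onset days it is 0.997^546 = 0.19 to 0.99^546 = 0.004 if days are independent; clustering of high-use days within patients would raise this.

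Cost: SAP wording, one redrawn figure and one model on data already collected. The short-term risk may look lower. The odds ratio may be imprecise: with the Protocol 3.3 inputs (about 4-7% of CAE-free days above 12), simulated clustered standard errors of the log odds ratio are 0.283-0.411. The 95% CI is then the estimate multiplied and divided by exp(1.96 x 0.283) = 1.7 to exp(1.96 x 0.411) = 2.2.
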